4.3.1 Screening Phase

The Screening Phase will be 3-14 days and will have 1 scheduled visit, the Screening Visit, which should be completed in person. Subjects will undergo all screening procedures as detailed in [Table 1](#).

Before any study procedures are performed, subjects must provide documented informed consent. After informed consent, subjects will be enrolled in the IWRS system. The subject's migraine history and medical history will be collected at the Screening Visit.

All subjects will continue to use their standard of care migraine medications (both prophylactic and acute, prescribed and OTC) during the Screening Phase. Subjects will record all concomitant medications, including standard of care migraine medications (both prophylactic and acute, prescribed and OTC), in a concomitant medication paper diary.

The duration between the Screening Visit and the Baseline Visit is 3-14 days. Every effort should be made to perform the Baseline Visit after as soon as the screening laboratory results are available and within the 14 days.

Individuals who do not meet the criteria for participation in this study (screen failure) may be considered for re-screening in select circumstances (e.g., previously pregnant, screening window too long). Subjects who were considered screen failures previously may be considered for re-screening provided the ineligibility was due to one of the eligibility criteria that may have changed due to medical intervention or one of the eligibility criteria modified in a protocol amendment. Adequate documentation in source records must support the previously failed criteria. In all possible re-screening circumstances, the situation must be discussed with the Sponsor prior to re-screening, with approval in writing from the Sponsor prior to re-screening. If a subject is approved for re-screening, a new subject number must be obtained from the appropriate study-related system. Re-screening will only be permitted one time.

4.3.2 Open-label Treatment Phase

The Open-label Treatment Phase will be up to 24 weeks from the Baseline Visit through the Week 24 or EOT Visit.

During the Open-label Treatment Phase, subjects will be instructed that they must take 1 tablet of study drug (rimegepant 75 mg ODT) daily. If subjects have a migraine during the Open-label Treatment Phase, then they may treat the migraine with permitted acute migraine medication as needed (see [Section 5.5.2](#)) while continuing to take the study drug.

Subjects will continue to record all concomitant medications, including standard of care migraine medications (both prophylactic and acute, prescribed and OTC), taken during the entire Open-label Treatment Phase on a concomitant medication paper diary.

After the Baseline Visit, study visits will be approximately every 2 weeks during the first month and then every 4 weeks, until the Week 24 or EOT Visit (Table 1). At each visit, the concomitant medication paper diary will be reviewed by site staff for completeness and compliance. Study drug compliance and concomitant medication use will be reviewed at each visit and subjects will be dispensed additional study drug as needed. Unused, non-expired, partial wallets will be returned to the subjects for completion prior to starting a new wallet. Additional safety assessments (including laboratory tests and ECGs) will be performed per the schedule outlined in Table 1.

Due to the COVID-19 pandemic, visits may be conducted remotely (ex: telephone, telemedicine) unless specified otherwise, and must be documented within the source records as being conducted remotely. All procedures not able to be completed due to a visit being conducted remotely must be reported as a protocol deviation and can be performed at the next visit, where appropriate to do so based on subject presentation.

4.3.2.1 *Baseline Visit*

Once completing the Screening Phase, subjects will return to the study site for the Baseline Visit, which must be completed in person. Subjects who continue to meet all eligibility criteria and have been compliant with the concomitant medication paper diary may enter the Open-label Treatment Phase.

At the Baseline Visit, eligibility for continued participation in the study will be assessed before study drug is dispensed. Subjects will be instructed that they must take 1 tablet of study drug (rimegepant 75 mg ODT) each day, and dosing should occur around the same time for each scheduled dose. Subjects may start study drug on the day of the Baseline Visit or the following day, depending on the time of day of their visit. Subjects **must** be instructed that they CANNOT take more than 1 tablet of study drug daily during the Open-label Treatment Phase. If a dose of study drug for a given day is missed, lost, or otherwise unable to be taken, the subject should document that as a missed dose on the study drug wallet and should NOT take the following day's assigned dose until the next calendar day at the specified time.

4.3.2.2 *Week 24 or EOT Visit*

Subjects will return to the study site at the Week 24 Visit (Day 168 +/- 2 days), or at the EOT Visit for early discontinuation, for review of the concomitant medication paper diary, assessment of study drug compliance, and assessment of safety (including vital signs, laboratory tests, and electrocardiography) (Table 1). Subjects must return the unused study drug and concomitant paper diary to the study site.

All subjects **who take study drug and discontinue early from the Open-label Treatment Phase** should complete the EOT Visit. Otherwise, subjects should complete the Week 24 Visit.

In cases where a Week 24 or EOT Visit occurs remotely in order to be completed during the protocol required window and due to the COVID-19 pandemic, the subject should return to the site for the Follow-up Week 2 Visit (2 weeks after the Week 12 or EOT Visit, -2 to +14 days), to

complete all procedures that were not able to be completed remotely. Procedures completed at the Week 24 or EOT Visit occurring remotely do not need to be repeated.

4.3.3 *Follow-up Phase*

The Follow-up Phase will have 2 scheduled visits, Follow-up Week 2, and Follow-up Week 8; These visits should occur approximately 2 weeks and 8 weeks after the Week 24 or EOT Visit, respectively. All subjects ***who take study drug*** should complete both follow-up visits, regardless of completing the Open-label Treatment Phase.

Subjects will continue to record all concomitant medications, including standard of care migraine medications (both prophylactic and acute, prescribed and OTC), taken during the entire Follow-up Phase in a concomitant medication paper diary.

4.3.3.1 *Follow-up Week 2 Visit*

Subjects will return to the study site approximately 2 weeks (14 days +/- 2 days) after the Week 24 or EOT Visit to collect vital signs, LFTs, assessment of AEs/SAEs, to have the C-SSRS performed, and to have a urine pregnancy test performed (WOCBP).

Investigators should assess subjects for AEs consistent with drug dependency or withdrawal effects and report as appropriate (see [Section 7.4](#)).

4.3.3.2 *Follow-up Week 8 Visit*

Subjects will return to the study site approximately 8 weeks (56 days +/- 2 days) after the Week 24 or EOT Visit to collect vital signs, LFTs, assessment of AE/SAEs, and to have a serum pregnancy test performed (WOCBP). Subjects will return the concomitant medication paper diary for documenting concomitant medications.

The visit window for the Follow-up Week 8 Visit is 56 days +/- 2 days; however, in cases of a delayed visit due to restrictions resulting from the COVID-19 pandemic, + 14 days may be utilized instead of + 2 days in order to ensure this final visit is completed in person.

4.4 *Post Study Access to Therapy (if applicable)*

At the conclusion of this study, subjects or investigators will not have access to the study drug. The investigator should ensure that the subject receives appropriate standard of care to treat the condition under study.

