4.3 Schedule of Assessments

Every effort should be made to conduct the study visits as planned. Concerns related to the Coronavirus disease 2019 (COVID-19) pandemic, other natural catastrophes (e.g., hurricane), and any additional case-by-case situations may be discussed for approval with the Sponsor. Following approval, provisions may be implemented to minimize potential hazards to study subjects and to maintain compliance with local government and institutional guidance (e.g., study center has a policy that a clinical research visit must be delayed). These provisions may allow alternatives to in-person study visits and include, but are not limited to, the following: conducting remote study visits via phone/telemedicine video, focusing on safety assessments during remote visits, or performing safety labs via local laboratory or professional in-home phlebotomy vendors. Any potential issues should be discussed with Sponsor/CRO and will be addressed on an individualized basis. The Screening, Pre-Baseline Evaluation, Baseline, and Follow-up Week 8 Safety visits must be done in person. Other visits may be conducted under the provisions mentioned above (remote via phone/telemedicine, local labs, etc.).

Table 1 Schedule of Assessments

Procedure	Screening Phase (3-14 days)¹	Open-label Treatment Phase^{2,3}				Follow-up Phase²
	Screening Visit	Baseline Visit (Day 1)	Week 2 (Day 14 +/- 2 days)	Week 4 (Day 28), Week 8 (Day 56), Week 12 (Day 84), Week 16 (Day 112), & Week 20 (Day 140) (all visits +/- 2 days)	Week 24 (Day 168) (+/- 2 days) or EOT Visit	FU Week 2 and FU Week 8 Visits (both visits +/- 2 days) for all subjects⁴
Eligibility Assessments						
Informed Consent	X					
Duplicate Subject Check (in CTSdatabase)	X					
Inclusion/Exclusion Criteria	X	X				
Medical History	X					
Migraine History (signs/symptoms/prior treatment/frequency/intensity)	X					
Concomitant medication paper diary ⁵	X	X	X	X	X	X ⁵
Enroll subject / IWRS ⁶		X				
Safety Assessments						
Physical Examination ⁷	X			X (Week 12 Only)	X	
Vital Signs / Physical Measurements ⁸	X	X	X	X	X	X
Clinical Safety Laboratory Testing ⁹	X		X	X (Weeks 4, 8, 12, 16 Only)	X	
Liver Function Test (LFTs) ⁹	X	X	X	X	X	X
Lipid Panel ⁹		X		X (Week 12 only)	X	

Table 1 Schedule of Assessments

Procedure	Screening Phase (3-14 days) ¹	Open-label Treatment Phase ^{2,3}				Follow-up Phase ²

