The Columbia-Suicide Severity Rating Scale (C-SSRS) is a questionnaire used for suicide Assessment.⁹ The C-SSRS “Screening version” will be used at the Screening Visit and the “Since Last Visit version”¹⁰ will be used at subsequent visits in this study.

The C-SSRS Assessment is intended to help establish a person’s immediate risk of suicide. The C-SSRS is a clinician administered scale that should be administered by a certified rater. This scale will be collected on site with a paper form. The C-SSRS should be reviewed by the Investigator or designee before the subject is allowed to leave clinic.

At the Screening Visit, the recall period for completing is 12 months for suicidal ideation and 10 years for suicidal behavior; at all other visits, the recall period for completing the C-SSRS is since the last visit (Table 1).

Any “Yes” responses must be immediately evaluated by the investigator. If the Investigator determines that a subject is at risk of suicide, self-harm, appropriate measures to ensure the subject’s safety and obtain mental health evaluation must be implemented. In such circumstances, the subject must immediately be discontinued from the study. The event should be recorded as either an AE or SAE as determined by the Investigator and reported within 24 hours to the Sponsor.

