Process for abnormal liver function tests: If at any visit after initiation of study drug the AST or ALT is $> 3x$ ULN, the following steps should be taken as soon as the investigator is aware: 1. The subject must be informed of the results and instructed to stop study drug, 2. The subject must be instructed to return to the clinic within 3-5 days for Unscheduled visit for repeat LFT panel and further clinical evaluation and testing as appropriate (with consultation with the Medical Monitor, and 3. The Medical Monitor and Pfizer Medical Monitor (if separate) should immediately be contacted. Guidance will be provided to augment management as appropriate.

8.5 Environmental Exposure, Exposure During Pregnancy or Breastfeeding, and Occupational Exposure

Environmental exposure occurs when a person not enrolled in the study as a subject receives

unplanned direct contact with or exposure to the study drug. Such exposure may or may not lead to the occurrence of an AE or SAE. Persons at risk for environmental exposure include healthcare providers, family members, and others who may be exposed. An environmental exposure may include EDP, EDB, and occupational exposure.

Any such exposures to the study drug under study are reportable to Pfizer Safety within 24 hours of investigator awareness.

8.5.1 *Exposure During Pregnancy*

If, following the Baseline Visit it is subsequently discovered that a study subject is pregnant or may have been pregnant at the time of the investigational product exposure, including during at least 6 half-lives after the product administration, the investigational product will be permanently discontinued in an appropriate manner (i.e., dose tapering if necessary for subject safety). Protocol-required procedures for the study discontinued and the follow-up must be performed on the subject unless contraindicated by the pregnancy (i.e., x-ray studies). Other appropriate pregnancy follow-up procedures should be considered if indicated. The investigator must immediately notify the Pfizer (or designee) Medical Monitor and report the event by either using the PSSA tool and by completing an Exposure During Pregnancy (EDP) Supplemental Form following the SAE reporting procedures as described in [Section 8.1.2](#).

Follow-up information regarding the course of the pregnancy, including perinatal and neonatal outcome and, where applicable offspring information must be reported on an EDP Supplemental Form.

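### If the C-SSRS is not done at a remote visit, the recall rule leaves the interval before that visit covered by no C-SSRS form

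*Protocol*

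**What the plan says.** Protocol 6.2.5 fixes both the place and the recall of the C-SSRS. On place: "This scale will be collected on site with a paper form", and "The C-SSRS should be reviewed by the Investigator or designee before the subject is allowed to leave clinic". On recall, after Screening: "at all other visits, the recall period for completing the C-SSRS is since the last visit". SAP 6.4.5 repeats the recall rule and says the scale is given at every visit except Follow-up Week 8.

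Protocol 4.3 requires Screening, Pre-Baseline Evaluation, Baseline and Follow-up Week 8 to be in person. For the rest: "Other visits may be conducted under the provisions mentioned above (remote via phone/telemedicine, local labs, etc". Week 2 to Week 24 and Follow-up Week 2 can therefore be remote, subject to sponsor approval. The listed provisions include "conducting remote study visits via phone/telemedicine video, focusing on safety assessments during remote visits".

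For what cannot be done at a remote treatment visit, Protocol 4.3.2 says: "All procedures not able to be completed due to a visit being conducted remotely must be reported as a protocol deviation". The same sentence goes on: "and can be performed at the next visit, where appropriate to do so based on subject presentation". Protocol 4.3.2.2 adds a rule for a remote Week 24 or EOT Visit: the subject should come to the site at Follow-up Week 2 for whatever could not be done remotely.

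**The concern.** The recall rule assumes that the last visit and the last C-SSRS are the same contact. They part company when a visit takes place without the scale. The documents call a remote contact a visit, so it resets the start of recall even if no C-SSRS was done there. The next form then does not reach back over the missed interval.

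Exploratory objective 6 is at stake: the number and percentage of subjects with suicidal ideation, suicidal behavior or self-injury on treatment. SAP Table 2 takes as denominator the safety subjects with C-SSRS data on treatment, and SAP 6.1.3 uses observed data without imputation. A subject with one uncovered interval and other forms on file stays in the denominator, and the gap is indistinguishable from a negative answer. SAP 6.4.5 plans frequency tables only and says nothing about reporting missed assessments; table contents are deferred to the Core SAP, which is not among the documents.

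**Working it through.** The plan states no figure on this point to reproduce. The check sets the rules side by side and then measures the interval.

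**1. How the gap arises.** Suppose Week 8 is remote and no C-SSRS is done.
- The Week 4 form covers Week 2 to Week 4.
- At Week 12 the last visit is the remote Week 8, so the Week 12 form covers Week 8 to Week 12.
- No form covers Week 4 to Week 8.

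**2. Whether the catch-up closes it.** Protocol 4.3.2 permits catch-up but does not require it. Table 1 already schedules a C-SSRS at Week 12, so a catch-up there coincides with the form already due. No text moves the start of recall back to Week 4.

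**3. Length of the gap.** Inputs: scheduled days 1, 14, 28, 56, 84, 112, 140 and 168 (Protocol Table 1). Formula: day of the remote visit minus day of the preceding visit.
- Remote Week 2: 14 − 1 = 13 days; 13/168 = 7.7% of the treatment phase.
- Remote Week 4: 28 − 14 = 14 days; 14/168 = 8.3%.
- Remote Week 8, 12, 16, 20 or 24: 28 days; 28/168 = 16.7%.

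**4. Remote Week 24 Visit.** Protocol 4.3.2.2 places the catch-up at 2 weeks, −2 to +14 days, so 14 − 2 = 12 to 14 + 14 = 28 days after the visit. SAP 3.2 ends the on-treatment period 7 days after discontinuation. If dosing ended about Week 24, the catch-up form falls 12 − 7 = 5 to 28 − 7 = 21 days after that limit. SAP 7.2 assigns measurements to periods by date, and SAP Table 3 opens Follow-up Week 2 at follow-up day 8. A finding on that form would count as follow-up and not under objective 6. The start of recall is also unchanged, so Week 20 to Week 24 is not asked about. (The catch-up sentence in 4.3.2.2 counts its 2 weeks from the Week 12 or EOT Visit although the section concerns Week 24; the two need to be reconciled.)

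**5. Ceiling on the effect.** The share p of Week 2 to Week 24 visits held remotely without a C-SSRS is not in the documents. Taking p as an assumption, equal across visits, the expected uncovered time for a full-term subject is p × (13 + 14 + 5 × 28) = p × 167 days:
- p = 5%: 8.35 days
- p = 10%: 16.7 days
- p = 20%: 33.4 days

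If findings are spread evenly over treatment, the share of subjects with a finding who are missed is at most p. It reaches p only if each such subject's sole finding lies wholly inside a gap. A finding that lasts into a covered interval, or recurs in one, still counts the subject.

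**The case against.** The strongest reply is that no text says the C-SSRS is dropped at a remote visit. The scale is clinician administered, Table 1 lists it as a safety assessment, and remote visits are to focus on safety. A rater could complete the paper form by phone or video. This stands as far as it goes: omission is inferred from the on-site, paper and before-leaving-clinic wording. But no passage provides for remote administration either, so a site following 6.2.5 literally would skip the scale.

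Second, the recall wording follows the name of the form, and a certified rater may look back to the last completed form after a miss. That is possible, but nothing instructs it, and the rater training is not in the documents.

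Third, suicidality is captured elsewhere. Adverse events are assessed at every visit, the SAP tabulates suicidality events, and SAP 6.4.6 lists such subjects for narratives. This is real but partial, because Protocol section 8 tells sites not to question subjects about specific events.

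Three stronger readings are tempting, and the documents do not support them.
- A reader might infer that the interval is never assessed for suicidality. Continued adverse event collection, and the possibility of a rater looking back, rule that out as a flat statement.
- A reader might infer that every unscheduled visit opens the same gap. Protocol 8.4 does require one for raised transaminases: "The subject must be instructed to return to the clinic within 3-5 days for Unscheduled visit for repeat LFT panel". But that visit is in the clinic, nothing prevents a C-SSRS there, and the statement in SAP 6.4.5 that the scale is given at all visits except one may include it.
- A reader might infer that findings are understated in proportion to missed time. For an endpoint counting subjects with any finding, that is a ceiling and not an estimate.

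**Conclusion.** The gap is real on the text but narrow. It needs two conditions: that the C-SSRS is not done at a remote visit, and that raters apply the recall rule as written. Each missed assessment then leaves 13 to 28 days without a C-SSRS question, about 8% to 17% of the 168-day treatment phase. Any resulting error lowers the count for objective 6. Its size is unknown.

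The objective is exploratory and descriptive, and the primary endpoint is untouched. Remote visits are meant to be exceptions. The point is therefore minor, but worth making because the stated rule works against its purpose exactly when an assessment has been missed.

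**What to change.** In Protocol 6.2.5 and SAP 6.4.5, change the recall period after Screening from *since the last visit* to *since the last completed C-SSRS*. Tell raters to apply the Since Last Visit form that way after any contact, remote or unscheduled, at which no C-SSRS was done. Where raters already do this, nothing changes; where they do not, the next form covers the missed interval.

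The change does not alter how the SAP dates a form completed at Follow-up Week 2 after a remote Week 24 or EOT Visit. One sentence in SAP 6.4.5 saying in which period such a form counts would settle that.

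The cost is a phrase in each document and a rater reminder, with no extra visit or procedure. The small downside is a longer recall period after a missed assessment.

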5 POPULATION

5.1 Number of Subjects

A sufficient number of subjects will be screened to treat approximately 285 subjects with study drug to ensure that at least 170 subjects will complete 24 weeks of treatment. All subjects will be assigned to rimegepant 75 mg ODT dosed daily.

5.2 Inclusion Criteria

1. Target Population

Subject has at least 1 year history of episodic migraine (with or without aura) consistent with a diagnosis according to the International Classification of Headache Disorders, 3rd Edition⁷, including the following:

- a) Age of onset of migraines prior to 50 years of age.
- b) Migraine attacks, on average, lasting 4 - 72 hours if untreated.
- c) Per subject report, 4-14 migraine attacks of moderate or severe intensity per month within the last 3 months prior to the Screening Visit (month is defined as 4 weeks for the purpose of this protocol).
- d) Ability to distinguish migraine attacks from tension/cluster headaches.
- e) Subjects on prophylactic migraine medication are permitted to remain on therapy if the dose has been stable for at least 3 months (12 weeks) prior to the Screening Visit, and the dose is not expected to change during the course of the study.
 - i. Subjects may remain on one (1) medication with possible migraine-prophylactic effects (see [Section 5.4](#)).
 - ii. Concomitant use of a CGRP antagonist, such as rimegepant (Nurtec[®] ODT), erenumab (AimovigTM), fremanezumab (AjovyTM), atogepant (QuliptaTM), ubrogepant (UbrelvyTM), galcanezumab (EmgalityTM), or eptinezumab (VygepiTM) is prohibited.
 - iii. Subjects who previously discontinued oral prophylactic migraine medication must have done so at least 30 days prior to the Screening Visit.
 - iv. Subjects who previously discontinued biologic migraine medication must have done so at least 3 months (12 weeks) prior to the Screening Visit.
- f) Subjects with contraindications for use of triptans may be included provided they meet all other study entry criteria.

2. Age and Reproductive Status
 - a) Subjects \geq 18 years.
 - b) Subject meets reproductive criteria. Refer to [Appendix 5](#) for reproductive criteria for male ([Section 16.5.1](#)) and female ([Section 16.5.2](#)) subjects.
 - c) At the Baseline Visit, WOCBP must have a negative pregnancy test (minimum sensitivity 25 IU/L or equivalent units of HCG) before dosing with study drug.
3. No clinically significant abnormality identified on the medical or laboratory evaluation. A subject with a clinical abnormality or laboratory parameters outside the reference range may be included only if the investigator considers the finding not clinically significant, that it will not introduce additional risk factors, nor interfere with the study procedures (not including exclusion criteria listed in [Section 5.3](#)).

